This search will use ICD-10 codes as defined by the UK biobank Outcome Adjudication Group (Definitions of Stroke for UK Biobank Phase 1 Outcomes Adjudication Date: August 2017 Version: 1.1 https://biobank.ndph.ox.ac.uk/showcase/showcase/docs/alg_outcome_stroke.pdf). This will identify the following events:

- 1. Admission to hospital with aneurysmal subarachnoid haemorrhage (I60.0-I60.7)
- 2. Occlusive treatment of aneurysm.
- 3. Death diagnosed as subarachnoid haemorrhage in parts 1a-c of the death certificate.

All patients identified from the HES search with any of the above events will then have their medical notes re-evaluated by the local neurosurgery unit to confirm the HES report has accurately identified the event as aneurysm rupture or treatment.

A similar search will be repeated in Wales using NWIS/PEDW where NHS numbers are also used. Scotland does not use NHS numbers making searches more complex. However, a further search of equivalent database (SMR01) will be performed in Scotland using name and date of birth for identification.

Data collection - quality assurance - central HES ONS data

Additionally, all patients will be checked for possible SAH events that could have been miscoded.

Therefore, any patients with the codes:

- 1. Subarachnoid haemorrhage (other and unspecified) (I60.8-60.9)
- 2. Intracerebral haemorrhage (including intraventricular haemorrhage (I61.0-61.9)
- 3. Non-traumatic subdural haemorrhage (I62.00-I62.02)
- 4. Traumatic subarachnoid haemorrhage (S06.6X0, S06.6X9A, S06.6X9, S06.6X8A)

will have their casenotes reviewed for evidence the haemorrhage was aneurysmal.

Any patients with the following codes:

- 5. I46.1 sudden cardiac death
- 6. R96 other sudden death cause unknown
- 7. R98 unattended death

will have their casenotes reviewed to assess if their death was likely due rupture of their aneurysm.

Additionally, in at least one pilot site, all patients with the code

8. Cerebral infarction (63.0-63.9 & I64.X)

will have their casenotes reviewed to estimate rates of missed diagnosis for the whole cohort.

Where verification cannot be established from medical notes, any patients with codes in the specified possible miscoded SAH events will be assumed to be non-aneurysmal unless they have a procedure code indicating occlusive treatment of aneurysm within 30 days after the event, or they were coded as

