subarachnoid haemorrhage other or unspecified and they subsequently died within 30 days (based on the very low rate of mortality from non-aneurysmal SAH) and did not have any additional codes for trauma indicating a non-aneurysmal event.

Data collection - other considerations - central HES ONS data

Last follow-up for each patient will be set as the time at which the HES search was performed, or the patient was unregistered with a GP in the UK or date of death, or the aneurysm was treated, whichever is earliest.

Additionally, we will record

- 1. race
- 2. I10 essential (primary) hypertension
- 3. Z72.0 tobacco use
- 4. F17.2 tobacco dependence

And use these to complete any missing baseline data. Where baseline data and HES conflict, the baseline data will be used. Where neither is available, after assessment for any bias (missing completely at random MCAR, missing at random MAR, missing not at random MNAR) multiple imputation will be used.

Statistical analysis - Aim 1 - PHASES validation

The PHASES study provides the coefficients from their Cox regression model and baseline survival at 5 years that allows the absolute 5-year risk of rupture, to be calculated for all patients who are not censored before 5 years, using age, whether the patients has hypertension, history of SAH, size of aneurysm (3 categories) and location of aneurysm. The time to censoring will be calculated (death or date of HES search or date unregistered from GP practice whichever is first) to ensure 5 years of follow up if rupture has not occurred. Discrimination will be assessed using Harrell's C-index of concordance and Royston and Sauerbrei's D statistic. Calibration will be assessed at the 5 year time point using the method in Royston (2014). These will be used to calculate the number of SAH events per 5 years for each PHASES score (0 to 12+) and expressed as a percentage with 95% confidence interval to compare to the PHASES estimates.

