There are multiple potential causes leading to underestimates of rupture risk. The magnitude of these will be estimated and corrected for. In view that all SAH events will be verified in clinical notes it is not expected that there will be any significant overestimation and consequently correction. Events may be missed due to migration. Any patients noted at time of baseline data collection to have emigrated will have this recorded and this will be used for censoring. Additionally, HES data will reveal any patients who have unregistered with their GP for emigration which will be used as a censoring event. Unfortunately, it is anticipated that not all patients will unregister on departure from the UK and therefore the observed emigration rate (that from the baseline data collection and HES data) will be subtracted from average national migration figures and this applied to the data.

Events may be missed due to miscoding. Aneurysmal SAH miscoded as:

1. Cerebral infarction (63.0-63.9 & I64.X)

Will be identified at one or more test sites by review of clinical notes to estimate any under-estimates due to miscoding and these estimates applied to the whole cohort.

In the event there are high rates of failed verification for the codes:

- 1. Intracerebral haemorrhage (including intraventricular haemorrhage (I61.0-61.9)
- 2. Subarachnoid haemorrhage (other and unspecified) (I60.8-60.9)
- 3. Non-traumatic subdural haemorrhage (I62.00-I62.02)
- 4. Traumatic subarachnoid haemorrhage (S06.6X0, S06.6X9A, S06.6X9, S06.6X8A)
- 5. I46.1 sudden cardiac death R98 unattended death
- 6. R96 other sudden death cause unknown
- 7. R98 unattended death

at some centres, then error estimates may be applied to the data from centres with robust code verification.

Additionally, at baseline data collection, any subsequent SAH events observed in the local notes will be recorded with their date, or date of last follow up. The SAH events observed during this follow up period will be compared to that for the similar period using HES data (after applying the above corrections), and the total risk estimates adjusted for any differences between these to give final 5 year risk estimates.

Discrimination will be assessed with the C statistic but is expected to be poor due to low event rates and therefore will be compared to the original PHASES data. Calibration will be assessed with calibration plots and Hosmer-Lemeshow tests.

Statistical analysis – Aim 2 - Additional prognostic factors

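### The correction for unverifiable haemorrhage and sudden-death codes is optional, conditional and ambiguously aimed, although the same section promises that underestimates will be corrected

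*Protocol*

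**What the plan says.** Two parts of Section 5 of the protocol bear on this.

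*Data collection – quality assurance – central HES ONS data* lists codes that may hide a rupture: I60.8–I60.9, I61, I62, S06.6, and the sudden-death codes I46.1, R96 and R98. Case notes are reviewed for each. Where the notes do not settle the matter, "any patients with codes in the specified possible miscoded SAH events will be assumed to be non-aneurysmal unless they have a procedure code" for occlusive treatment within 30 days. The second exception is a code of "subarachnoid haemorrhage other or unspecified and they subsequently died within 30 days", with no trauma code.

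*Statistical analysis – Aim 1 – PHASES validation* acknowledges that rupture risk may be underestimated for several reasons and commits itself: "The magnitude of these will be estimated and corrected for". For aneurysmal bleeds coded as cerebral infarction, one or more test sites review notes "to estimate any under-estimates due to miscoding and these estimates applied to the whole cohort". For the codes listed above the rule is different. It begins "In the event there are high rates of failed verification for the codes" and ends "at some centres, then error estimates may be applied to the data from centres with robust code verification".

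Two later steps are relevant. Aim 1 compares ruptures seen in local notes with the corrected HES ruptures over a similar period and adjusts the total risk estimates for the difference. Aim 2 adds a sensitivity model whose outcome is rupture or an R96/R98 death.

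**The concern.** The default rule can err in one direction only: an unverifiable record that was truly a rupture becomes a non-event. The correction meant to offset this has three weaknesses in its wording.

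- **Optional.** It uses *may*, where the opening of the same text says *will*.
- **Conditional.** It starts only when failure is high at some centres, so moderate failure triggers nothing.
- **Unclear target.** Read grammatically, the estimates go to the data of centres whose verification worked.

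Failed verification is foreseeable. Section 3 says that ruptures cannot be identified from neurosciences records because many patients are admitted elsewhere, and Section 5 gives district-hospital events and pre-hospital deaths as the reason for the linkage. Those are the records a neurosurgical unit is least likely to be able to check.

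At stake are the 5-year risks by PHASES score and the calibration of PHASES in the UK, which would depend partly on how well each unit can trace old notes.

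**Working it through.** **1. Which records fall through.** Apply the default and its two exceptions to unverifiable records:

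| Unverifiable record | Status |
|---|---|
| Any listed code, occlusive treatment within 30 days | rescued |
| I60.8–I60.9, death within 30 days, no trauma code | rescued |
| I60.8–I60.9, survivor, no occlusive treatment | non-event |
| I61 or I62, fatal, no occlusive treatment | non-event |
| I46.1, R96 or R98 death, no occlusive treatment | non-event |

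The exceptions help, but they leave whole groups uncorrected.

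**2. Scale from the protocol.** Section 7.2.1 uses 51 ruptures in 1,692 patients over 4.1 years.

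- Sixty events: 60 × 1692/51 = 1,990.6 patients, and × 4.1 = 8,161 patient-years. This reproduces the stated 1,990 and 8,161.
- Rate: 51/(1692 × 4.1) = 0.735% per year, so T = 5 × 0.735% ≈ 3.68% over 5 years.

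**3. Size of the loss.** The protocol gives none of the next four inputs. All are assumed ranges:

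- f = share of true ruptures recorded under a listed code: 0.1–0.3
- u = share of those unverifiable at failing centres: 0.3–0.6
- r = share of the unverifiable rescued by the two exceptions: 0–0.5
- c = share of all ruptures that occur at failing centres: 0.25–0.5

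Loss at a failing centre: L = f × u × (1 − r).

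- Smallest: 0.1 × 0.3 × 0.5 = 0.015
- Largest: 0.3 × 0.6 × 1 = 0.18

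Failing-centre 5-year risk, T(1 − L): 3.62% down to 3.01%, against 3.68%.

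Pooled relative bias with no correction, −c × L:

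- Smallest: 0.25 × 0.015 = 0.4%
- Largest: 0.5 × 0.18 = 9.0%

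On the Aim 1 target of 60 events this is 60 × 0.00375 ≈ 0.2 to 60 × 0.09 = 5.4 ruptures.

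**4. Below the trigger.** If u is only 0.1–0.2 and is not judged high, and with r = 0, the loss at those centres is 0.1 × 0.1 = 1% to 0.3 × 0.2 = 6%. This rule then corrects none of it.

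**5. The literal wording.** Suppose the data of robust centres are inflated by 1/(1 − L) and failing centres are left alone.

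- Robust centres rise to between 3.73% (3.676/0.985) and 4.48% (3.676/0.82).
- Failing centres stay at 3.01%–3.62%.
- Pooled factor: (1 − c)/(1 − L) + c(1 − L). At c = 0.5, L = 0.015 this is 1.000. At c = 0.25, L = 0.18 it is 0.915 + 0.205 = 1.120.

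Pooled bias therefore runs from about 0% to +12%. On this reading the pooled figure need not be low, but both groups of centres are wrong.

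**The case against.** A reader might infer that the plan deliberately corrects the wrong centres. The documents do not support that. The phrase about robust verification can equally describe where the estimates come from, and the infarction rule just above it runs from test sites to the whole cohort. A wording slip is the likelier explanation.

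A reader might also infer that lost ruptures stay lost throughout, or that a downward bias is guaranteed. That too goes beyond the text. Admissions coded I60.0–I60.7 and deaths certified as subarachnoid haemorrhage are on the main event list, and the non-event default is not written for them. The comparison with local notes has no trigger and can raise the total risk estimates. The R96/R98 model addresses some unresolved deaths.

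These safeguards are limited. The local-notes step acts on totals, covers only local follow-up, and relies on records at the same centres where verification failed. The R96/R98 model is an Aim 2 sensitivity analysis and omits the haemorrhage codes and I46.1. Neither rescores individual patients for the C-index, D statistic, calibration or main Cox models.

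Finally, a numerical threshold for high failure, and the mechanics of applying the estimates, can properly be left to a statistical analysis plan. That is fair, and their absence is not the point here. The protocol sentence would still be optional, conditional and unclear about its target, against an unconditional promise in the same text.

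**Conclusion.** The point holds as a defect in a stated rule. Unverifiable records default to non-events apart from two exceptions. The only correction specific to them is optional, conditional on an undefined level of failure, and open to being read as aimed at the wrong centres. This conflicts with the commitment that underestimates will be estimated and corrected. Followed as written, the rule leaves ruptures under-counted at patient level at centres with failed verification, and the later steps mitigate this only in part.

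The size cannot be derived from the protocol. The relative shortfall of about 0.4% to 9% in the uncorrected pooled 5-year risk rests wholly on the assumed ranges for f, u, r and c, and is taken before any local-notes adjustment. The direction of the loss at failing centres is more certain than its amount. The change should be made, but the text does not show a planned wrong-way correction.

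**What to change.** Replace the sentence under Aim 1 with:

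*Confirmation proportions by code group, estimated from verified records, will be applied to all unverified records in the listed code groups at every centre.*

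Drop the trigger and the word *may*. State whether records that meet one of the two exceptions keep the status those exceptions give them.

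Preferably carry this out by multiple imputation of rupture status, with predictors such as age, death within 30 days and a trauma code. Patient-level outcomes and their uncertainty then enter Aims 1 to 3. Keep the current non-event default as a sensitivity analysis.

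The cost is a wording change, modest analysis work and slightly wider intervals. The imputation already planned covers baseline and covariate data only, so this extends it to the outcome. It also assumes that unverified records resemble verified ones given the predictors. That may fail if notes are harder to trace for certain kinds of event, which is one reason to keep the sensitivity analysis.

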The strength of using national databases is that they will capture any event of aneurysm rupture irrespective where it occurs in the UK. Rupture is a sudden severe event that always results in a hospital admission or death and it is not anticipated that there is a significant rate of SAH undiagnosed in the community. Rupture could not be identified from the neurosciences records however as many patients who suffer rupture of their aneurysm will be admitted to another hospital (e.g. their local hospital is not a neurosciences centre, or they have moved home, etc). These databases are also linked to ONS and so can capture causes of death for patients who die before reaching hospital. The comprehensive coverage offered by these admission databases will recreate the high follow-up rates that are normally only achieved with a prospective study.

In the third stage local neurosurgery units will confirm the admissions identified in stage 2 were correctly coded as a subarachnoid haemorrhage. This will be a final quality control to mitigate for any issues with miscoding in HES/PEDW/SMR to and ensure the data derived is accurate and meaningful.

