- Population: European/North American, Finnish, Japanese (where race cannot be confirmed it will be assumed to be non-Finnish and non-Japanese on the basis that there is a low incidence of these populations in the UK and their presence would usually be considered noteworthy in a clinical note.

The additional desirable covariates at time of diagnosis will include:

- aspirin use any dose used >3* per week
- statin use any statin use >3* per week
- smoking history non-smoker, ex-smoker, current smoker
- Aneurysm multiplicity record number of intra-dural aneurysms the patient has (treated or untreated)
- Family history number of 1 first degree and second degree relatives with UIA/SAH
- History of Autosomal Dominant Polycystic Kidney Disease yes, no
- Aneurysm location subclassification ICA paraclinoid (ophthalmic and superior hypophyseal) ICA (PCom), ICA other (anterior choroidal and bifurcation), ACA ACOM, ACA pericallosal, MCA, Posterior (basilar termination), Posterior (SCA), Posterior (AICA) Posterior (PICA)
- Bleb or irregularity of aneurysm recorded as present or absent from radiology report only. If not mentioned in report assumed to be absent. If no radiology report available, then recorded as NA.
- New/known diagnosis: patients in whom the aneurysm was known prior to the search period will be recorded as known diagnosis and otherwise as new diagnosis.

Data collection – aneurysm rupture/censoring events – local neurosciences units

At the time of baseline data collection locally available follow up will be recorded which will include:

• Date of last follow-up

- Date of death (if applicable)
- Cause of death (if applicable)
- Date of SAH (if applicable)
- Location of aneurysm causing SAH (if applicable)
- Date of aneurysm treatment (if applicable)
- Reason for aneurysm treatment (if applicable)

This data will be used for quality control of subsequent HES searches.

Data collection - aneurysm rupture/censoring events - central HES ONS data

Upon collection of all baseline data, a search of the Hospital Episode Statistics (HES) and Office for National Statistics (ONS) databases using the patient's NHS numbers be conducted. The use of a HES and ONS search is designed to maximise the identification of rupture events which are not treated in neurosurgical unit as subarachnoid haemorrhage. It will thus identify events managed in a district general hospital or those who die pre-hospital.

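### Aim 1 adjusts the final 5-year risks, in no stated direction, for differences from local-notes SAH counts, a source the protocol says cannot identify rupture

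*Protocol*

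**What the plan says.** All of this is in the protocol.

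- **Section 5, Statistical analysis, Aim 1.** The text lists causes of underestimated rupture risk and plans a correction for each. Emigration is corrected from national figures. Infarction miscoding is reviewed at one or more test sites, "to estimate any under-estimates due to miscoding and these estimates applied to the whole cohort". The last step compares SAH events seen in local notes, up to the last local follow-up, with corrected HES events for the similar period, "and the total risk estimates adjusted for any differences between these to give final 5 year risk estimates".
- **Section 3, Theoretical framework.** "Rupture could not be identified from the neurosciences records". The reason given is that many patients who rupture are admitted to a different hospital. This is the case for using national databases.
- **Section 5, local data on rupture and censoring events.** On the locally recorded follow-up, SAH and death data: "This data will be used for quality control of subsequent HES searches". No role in altering the risk estimate is mentioned there.
- **Section 5, Aim 1, on overestimation.** "In view that all SAH events will be verified in clinical notes it is not expected that there will be any significant overestimation".
- **Section 5, quality assurance of HES/ONS data.** A fallback rule begins "Where verification cannot be established from medical notes". Possible miscoded events are then taken as non-aneurysmal, with two exceptions that count as aneurysmal: an occlusive-treatment code within 30 days, or a code of other/unspecified SAH (I60.8-I60.9) followed by death within 30 days with no trauma code.

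**The concern.** The protocol uses HES/ONS because local records miss ruptures. It then lets a comparison with those local records change the headline result. The step has neither a sign nor a formula. If local notes show fewer events than HES, as section 3 leads one to expect, the wording allows the final risk to be lowered toward the less complete source.

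Comparing totals has a second weakness. Events missed by HES and events missed locally offset one another, so a zero difference does not show that either source is complete.

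Aim 1 sets absolute 5-year risk against the PHASES estimates. A shift produced by this step could be read as miscalibration of PHASES in UK patients.

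The verification premise is a smaller, separate matter. It is the stated ground for planning no correction for overestimation, and the fallback rule contradicts it.

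**Working it through.** **1. Planning rate (section 7.2.1).** Inputs: 51 ruptures, 1,692 patients, 4.1 years.
- The plan's own figure: 60/51 × 1,692 = 1,990.6 patients, and × 4.1 = 8,161.4 years. Stated: 1,990 and 8,161. It reproduces.
- Rate: 51/(1,692 × 4.1) = 51/6,937.2 = 0.735% per year.
- 5-year risk at constant hazard: 1 − exp(−5 × 0.00735) = 3.61%.

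**2. Effect of a proportional adjustment (one possible reading).** Let s be local events divided by HES events in the matched window. The documents give no value, so s is assumed. Adjusted risk = 1 − exp(−5 × 0.00735 × s).

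| s | Final 5-year risk |
|---|---|
| 1.1 | 3.96% |
| 1.0 | 3.61% |
| 0.9 | 3.25% |
| 0.8 | 2.90% |
| 0.7 | 2.54% |

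If HES is complete, s is the in-window local capture, and any value below 1 is bias. For scale, these are the exact Poisson 95% intervals around 3.61%:
- 60 events: 2.77-4.62%
- 120 events: 3.00-4.30%
- about 838 events (113,905 years × 0.00735): 3.38-3.86%

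At s = 0.7 the adjusted risk falls below all three. At s = 0.9 it falls below only the last.

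**3. Why counts cancel.** Let N be the true ruptures in the window, h the share missed by HES and l the share missed locally. HES finds N(1 − h) and local notes find N(1 − l). The difference is N(l − h), which is zero whenever l = h, however large both are.

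A patient-level union misses only events absent from both sources, a share h × l if misses are independent. With assumed values h = 0.05 and l = 0.30:
- union: 1 − 0.05 × 0.30 = 98.5%
- HES alone: 95%
- scaled to local counts: 70%

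If misses tend to fall on the same patients the union gains less, but it cannot fall below HES alone.

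**4. Verification.** The Aim 1 text rests on every SAH event being verified. The quality-assurance text provides for events that cannot be verified and counts two classes of them as ruptures. Both statements cannot hold. No size can be computed, because the documents give no expected number of such events.

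**The case against.** **Direction.** The adjustment closes a list of causes of underestimation. Read there, it may mean only adding SAHs seen locally that HES missed, which is close to the remedy below. A reader might infer that final risks will be rescaled to match local counts; the text does not say so. This stands. But the wording covers differences in either direction, so the downward reading is not excluded.

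**Matched window.** The comparison stops at the last local follow-up. A rupture elsewhere after that date creates no difference, and one before a later local contact may well have reached the notes. In-window capture is therefore plausibly higher than capture over all follow-up. This stands, and it means the table in the working is not a forecast.

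**Verification.** The default for unverifiable possible-miscoded events is non-aneurysmal, the exceptions are narrow, and a reason is given for the 30-day death rule. The text denies only significant overestimation, and it allows error estimates from centres with robust verification if failed verification is common. This stands too: the point is a contradiction in the stated premise, not evidence of material inflation.

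**Intervals and comparison.** A reader might also infer that the 95% intervals will be too narrow because correction factors are treated as known. The protocol is silent on this and an analysis plan could settle it, so it is not an error shown here. Nor do the documents show that comparing corrected estimates with PHASES is wrong, or that uncorrected events must be primary; those are preferences.

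**Conclusion.** The point holds in a limited form. Sections 3 and 5 give the local data incompatible roles: a source unable to identify rupture, a quality-control check, and an input to the final 5-year risk. They must be reconciled. The rule permits, but does not require, a downward adjustment toward the less complete source, and a comparison of counts cannot detect offsetting misses.

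The size is unknown. The fall from 3.61% to 2.54-3.25% assumes complete HES, constant hazard, a proportional adjustment and in-window local capture of 70-90%, none of which the documents establish except the planning rate behind the 3.61%. It should not be quoted as expected bias.

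The conflict over verification is also real, but narrow and unquantified. The sample-size figures are unaffected.

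**What to change.** 1. Replace the final adjustment with a patient-level union. Each SAH in local notes that is verified as aneurysmal but missing from HES/ONS (or the Welsh or Scottish equivalent) is added as an event on its recorded date.
2. Report HES sensitivity as the share of verified local events found in HES.
3. State that risk estimates will never be scaled down to local counts.
4. Reword the claim that all SAH events will be verified so that it agrees with the fallback rule, and add a sensitivity analysis excluding events counted without verification.
5. Report the estimate from ascertained events beside any migration- or miscoding-corrected estimate.

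The cost is a rewording of Aim 1 and a little more analysis. No new data are needed, because the date of any SAH and the date of last follow-up are already collected locally.

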The only study with no selection or follow up bias is based on a cohort of Finnish patients (Juvela 2013). This found markedly different rupture rates with 26% of small anterior aneurysms (the most common type) rupturing over 30 years (versus 0% extrapolating data from ISUIA). There are three possible explanations for these differences – genetic, environmental or methodological differences between the studies. Despite not one published genetic study, the results have largely been ignored based on an assumption that the difference is genetic. This has been driven by historical data showing a higher incidence of SAH in Finland (29.9 per 100,000). This historical data has recently been discredited, however, and SAH incidence has been shown to be similar in Finland to the rest of the world (8.9 per 100,000) (Korja 2016). The Finnish natural history studies may therefore be more representative than previously assumed.

The only other large studies were conducted in Japanese populations (Sonobe 2010, Morita 2012). They again differed enormously in their design. There are obvious differences in race (the Japanese population is the only other population proposed to have a different rupture rate to the rest of the world), length of follow up (1-30 years), loss to follow up (up to 71% in the largest study of 6697 patients). They also showed much higher rates of rupture than ISUIA. However, it is again unclear to what extent this relates to genetic differences, environmental differences or methodological differences.

Despite the obvious limitations of combining studies with different populations, methodologies and results, the data from these studies have been pooled with ISUIA to produce the PHASES score (Greving 2014). From this a 6 item scoring system (population, hypertension, age, aneurysm site,

Health Research Authority

previous subarachnoid haemorrhage and aneurysm size) was developed to predict 5 year rupture risk in patients with a diagnosed UIA. It assumes the data is representative and accurate, and ascribes the differences in risk to population rather than study methodology.

It leaves UK clinicians with a practical conundrum. Should management of patients be based on:

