7.2 Sampling

7.2.1 Size of sample

Sample Size

There are no accepted methods for power calculation for validation studies of prognostic models. Therefore, usually the rule of thumb to have ten events for every covariate tested is applied.

For Aim 1, 6 covariates will be tested suggesting at least 60 SAHs will need to be captured. ISUIA recorded 51 ruptures in 1692 patients over 4.1 years. Sixty events may therefore be expected in 1,990 patients with 8,161 years of follow up.

For Aim 2, 120 events will need to be observed to account for the 6 additional commonly occurring covariates which would be expected in 3,981 patients with 16,332 years of follow up.

For autosomal dominant polycystic kidney disease (ADPKD) which has a low incidence, larger numbers of patients will be needed. Ten events in ADPKD are expected in 1360 patient years of follow up assuming the risk of SAH is not elevated and similar to the general population. However, 16,332 years follow up would only yield 195 years in patients with ADPKD (based on a population study which found 53/4436 IAs had ADPKD (Nurmonen 2017) and consistent with pilot data where 11/1025 cases examined to date had ADPKD). Therefore 113,905 years of follow up would be required to capture 10 ruptures amongst 1,340 years follow up in ADPKD patients. This would equate to 22,781 patients with 5 years of follow up (or applying the slightly looser rule of 5 events per prognostic factor this would require 56,952 years of follow up with 11,391 patients).

In a local pilot 1,415 cases were identified over 14 years in a population of 3 million with an anticipated 6,000 years of follow up. Extrapolating to England, Wales and Scotland 31,130 patients with 132,200 years follow up are available - well in excess of the target of 8,161 to validate PHASES in the general population, as well as the 16,332 to test the additional variables, but only just sufficient to answer the role of rarer predictors such as ADPKD. For reference PHASES was based on 29,166 years of patient follow up. Therefore, all cases that can be identified in England and Wales will be sought up to a maximum of 22,781.

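### Protocol section 5 (Aim 1) blames an expected poor C statistic on few ruptures and benchmarks it directly against PHASES; the reason is wrong and the benchmark is not like for like

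*Protocol*

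**What the plan says.** Section 5 of the protocol, under the Aim 1 statistical analysis, first names the measures: "Discrimination will be assessed using Harrell's C-index of concordance and Royston and Sauerbrei's D statistic". Calibration follows: "Calibration will be assessed at the 5 year time point using the method in Royston (2014"), together with observed 5-year risk at each PHASES score, with 95% confidence intervals, for comparison with the PHASES estimates. At the end of the same section the protocol returns to discrimination and says that the C statistic "is expected to be poor due to low event rates and therefore will be compared to the original PHASES data". It then adds "Calibration will be assessed with calibration plots and Hosmer-Lemeshow tests".

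Three other statements bear on the comparison:

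- Section 1 describes PHASES as a six-item score pooled from cohorts with different populations and results, and says that it "ascribes the differences in risk to population rather than study methodology".
- The baseline data list in section 5 codes Population, but "where race cannot be confirmed it will be assumed to be non-Finnish and non-Japanese", because the other groups are rare in the UK.
- The Aim 1 analysis lists age, hypertension, earlier SAH, size and location as the inputs to the PHASES prediction. Population is not in that list.

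**The concern.** The sentence does two things before any data are seen. It gives a cause for a poor result, and from that cause it derives a benchmark.

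The cause is not a property of the statistic. Harrell's C is the share of usable patient pairs that the score ranks correctly. Fewer events mean fewer pairs and more noise, but no downward shift. What lowers C is a narrower spread of predicted risk, or coefficients that rank UK patients less well.

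The benchmark mixes those two explanations. If predicted risk is less spread out in the UK cohort than in PHASES, C will be lower even when every coefficient is right. As written, a real loss of ranking could be put down to rarity, and a drop due to case mix could be read as loss of ranking. Validating PHASES is a primary aim, and section 1 says that 24 of 30 UK units use the score.

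**Working it through.** **1. The plan's own figures.** The sample-size section (7.2.1) states "ISUIA recorded 51 ruptures in 1692 patients over 4.1 years".
- Rate = 51 / (1,692 × 4.1) = 0.00735 per patient-year.
- Patients for 60 events = 60 / (51/1,692) = 1,990.6; × 4.1 = 8,161 years. Both match the protocol.

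**2. Expected ruptures here and in PHASES.** Inputs from section 7.2.1: 22,781 patients × 5 years = 113,905 years planned, and 29,166 years in PHASES. Section 1 cites a rupture rate of 1.4% a year.
- This study at the ISUIA rate: 113,905 × 0.00735 = 837.
- PHASES at the ISUIA rate: 29,166 × 0.00735 = 214. At 1.4%: 29,166 × 0.014 = 408.

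The figure of 837 is an upper guide at that rate, because the 5-year risk is "to be calculated for all patients who are not censored before 5 years". Even so, about half of the events (1 − 408/837 = 51%) would have to be lost before the count fell to the higher PHASES figure.

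**3. Does a low rate lower C?** The documents give neither the PHASES C nor the spread of its linear predictor, so this step is a simulation under stated assumptions: exponential proportional hazards, 5-year administrative censoring, normal linear predictor with SD 1.0, correct coefficients, 22,781 patients.

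| Annual rate | Mean C |
|---|---|
| 0.25% | 0.755 |
| 0.735% | 0.757 |
| 1.4% | 0.754 |
| 3% | 0.752 |

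With SD 0.75 instead, C was 0.70 to 0.71 for 5-year risks from 1% to 17%. The rate makes no material difference.

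**4. What the event count does change.** At 0.735% a year, the sampling SD of C is about 0.027 with 70 events and about 0.009 with 800. The approximate 95% half-widths are 1.96 × 0.027 = 0.05 and 1.96 × 0.009 = 0.02.

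**5. Can a direct comparison of C separate case mix from failure?** Same setting, at 0.735% a year:

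| Correct model, predictor SD | C | Predictor SD 1.0, true slope | C |
|---|---|---|---|
| 1.0 | 0.756 | 1.0 | 0.756 |
| 0.8 | 0.711 | 0.8 | 0.710 |
| 0.6 | 0.666 | 0.6 | 0.665 |
| 0.4 | 0.609 | 0.4 | 0.610 |

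The columns agree, so C alone cannot tell the two apart. D also depends on predictor spread and does not settle it.

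**6. Size of the Population effect.** With predictor SD 0.75 in one population, C is 0.70 to 0.71. Pooling populations with an assumed hazard ratio of 2 to 3 raises it to 0.717 to 0.730, a difference of about 0.01 to 0.03. This also depends on the assumed population shares. A repeat run with 30%, 50% or 70% of patients in the higher-risk population gave about 0.01 at hazard ratio 2 and up to about 0.04 at hazard ratio 3.

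**The case against.** The strongest reply is that the protocol already plans the analyses that separate the two explanations. Taking the SD 0.6 and slope 0.6 cases from step 5, both with C of about 0.665, predicted against observed 5-year risk (%) by fifth of predicted risk is:

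- Correct model, narrow case mix: 1.4/1.5, 2.2/2.0, 3.0/3.4, 4.2/3.8, 7.1/7.1.
- Weakened coefficients: 0.6/1.5, 1.3/2.0, 2.2/3.4, 3.8/3.8, 9.6/7.1.

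The planned calibration and risk-by-score table would show the second pattern, though less clearly at the 60-event minimum. This stands. A reader might infer that a failure of PHASES as a whole could be explained away; the documents do not support that.

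Other parts of the reply also stand:

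- Comparing C with the development value is ordinary practice, and an analysis plan not shown here could add a case-mix-corrected benchmark. It would still leave the wrong reason in the protocol.
- The protocol does not say how the original C was computed, so the contribution of Population to it is not known from the documents.
- A reader might infer that early treatment of high-risk aneurysms makes the UK case mix narrower than that of PHASES. Section 1 says that 72% of ISUIA patients were treated and that high-risk aneurysms were probably removed before entry there too, so the direction is not established.
- A reader might give discrimination equal weight with calibration in Aim 1. The protocol sets no such weighting and no threshold for C.

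**Conclusion.** Wrong as written. A low event rate affects the precision of C, not its expected value. At the planned size the protocol's figures imply more ruptures than PHASES had, so rarity should not be offered as the reason for a low C. If recruitment reached only the 60-event minimum, rarity would explain a wide interval but still not a low value.

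The comparison with the original C is not like for like, because PHASES pooled populations with different risks and this cohort is nearly constant on Population. The documents do not fix how large that difference is; the estimate of about 0.01 to 0.03 rests on the assumed predictor SD, hazard ratios and population shares. It is about the size of sampling noise at 70 events and would matter mainly near full enrolment. The consequence is confined to the conclusion on discrimination.

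**What to change.** In the Aim 1 analysis text of section 5:

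1. Delete the attribution of poor discrimination to the event rate.
2. Report C and D with 95% confidence intervals.
3. Compare C with the value expected in this cohort if the PHASES coefficients were correct, either as a model-based concordance or from outcomes simulated from PHASES on the UK covariates.
4. Interpret C together with the calibration slope and the calibration analyses already planned.
5. If the original PHASES C is quoted, state that it comes from a different, pooled case mix.

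The cost is a revised sentence or two and a small amount of computation. No new data are needed.
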